4.2.1 Rationale for Endpoints

4.2.1.1 Efficacy Endpoints

To assess longer-term glucose-lowering efficacy (weeks to months), A1C will be measured. Since A1C reflects average glucose concentrations over the past 3-4 months, this measure provides a more useful index of the glycemic efficacy of ertugliflozin than FPG alone. Moreover, A1C is the key glycemic parameter which correlates with reduction of risk of diabetic complications. FPG will be measured to characterize the time course of glucose control.

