9.1 Statistical Analysis Plan Summary

Key elements of the statistical analysis plan are summarized below; the comprehensive plan is provided in Sections 9.2 to 9.12.

Statistical Analysis Plan Summary

Study Design Overview	Ertugliflozin T2DM Pediatric Study		
Treatment Assignment	Participants will be randomized in a 2:1 ratio to the ertugliflozin 5 mg group or placebo group. Randomization will be stratified by age (10 to 14 years of age, 15 to 17 years of age) and insulin use (No, Yes). A second randomization at Visit 5/Week 12 will randomize eligible participants (Section 6.1) in the ertugliflozin 5 mg group in a 1:1 ratio to continue on ertugliflozin 5 mg or up-titrate to ertugliflozin 15 mg. The second randomization will be stratified by insulin use (No, Yes). An IA to assess PK may result in dropping the 15 mg dose group. If this occurs, the second randomization will be discontinued and the participants in the 15 mg group will be down-titrated to the 5 mg dose for the remainder of the study.		
Analysis Populations	Efficacy: Full Analysis Set (FAS) Safety: All Participants as Treated (APaT)		
Primary Endpoint	A1C: Change from baseline at Week 24		
Secondary Endpoints	A1C: Change from baseline at Week 54 FPG: Change from baseline at Week 24 and at Week 54		

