9.4.1 Efficacy Endpoints

The descriptions of the efficacy measurements and timepoints at which they are measured are described in Section 8.2 and Section 1.3. The efficacy endpoints to be analyzed are listed in Table 6.

The mapping of relative day ranges to Week is provided in Appendix 11.

PRODUCT: MK-8835

PROTOCOL/AMENDMENT NO.: 059-04

Table 6 Efficacy Variables/Endpoints

Primary

Change from Baseline in A1C at Week 24 (pooled ertugliflozin 5 mg and 15 mg versus placebo)

Key Secondary

Change from Baseline in A1C at Week 24 (dose-optimized ertugliflozin versus placebo, and ertugliflozin 5 mg versus placebo)

Secondary

Change from Baseline in A1C at Week 54

Change from Baseline in FPG at Week 24 and at Week 54

Exploratory

Change from Baseline in A1C at Week 12

Proportion of participants initiating glycemic rescue therapy by Week 24

Proportion of participants initiating glycemic rescue or intensification therapy by Week 54

Proportion of participants with A1C <7.0% (53 mmol/mol) at Week 54 among those who up-titrated from ertugliflozin 5 mg/day to 15 mg/day

At Week 24 and Week 54:

Proportion of participants with A1C <7.0% (53 mmol/mol)

Proportion of participants with A1C <6.5% (48 mmol/mol)

Proportion of participants with A1C <7.0% (53 mmol/mol) among those with a baseline A1C \geq 7.0% (53 mmol/mol)

Change from Baseline in:

- · Body weight
- BMI percentile
- A1C among participants who up-titrated from ertugliflozin 5 mg/day to 15 mg/day
- Systolic blood pressure
- Diastolic blood pressure
- Waist circumference
- Waist circumference to height ratio

A1C = glycosylated hemoglobin; BMI = body mass index; FPG = fasting plasma glucose.

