The RD analysis may not be feasible due to insufficient observed Week 24 data post discontinuation of study medication. If the number of RD participants per group is at least 50% of participants who discontinue from study medication per arm, then RD will be the primary approach to impute missing data for the TP estimand. If at least one group has either less than 50% RD participants or fewer than 5 total RD participants, then RD will not be performed, and WI will become the primary analysis method. If the minimum data requirement for the RD method is met, then WI will be implemented as a sensitivity approach for the TP estimand. The WI analysis assumes participants who prematurely discontinued from the study or who have an intermittent missing Week 24 value would have a 'washout' of any potential effect of the assigned study medication.

For all analyses involving simulated data, a seed of 8835059 will be used for random number generation.

A constrained longitudinal data analysis (cLDA) model, based on Liang and Zeger [Liang, K.-Y. and Zeger, S. L. 2000], will be used for analyses addressing the TE estimand for A1C mean change from baseline and FPG mean change from baseline. Time will be treated as a categorical variable so that no restriction is imposed on the trajectory of the means over time. The cLDA model will also adjust for treatment, the age stratum, the insulin use stratum, and the interaction of time by treatment. The cLDA model assumes a common mean across treatment groups at baseline within each age and insulin use category (due to randomization) but different means between categories, and a different mean for each treatment at each of the post-baseline timepoints. In the cLDA model, the response vector consists of baseline and the values observed at each post-baseline timepoint. The treatment difference in terms of mean change from baseline to a given timepoint will be estimated and tested from this model. An unstructured covariance matrix will be used to model the correlation among repeated measurements.

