For the cLDA model, the Kenward-Roger adjustment will be used with restricted (or residual) maximum likelihood (REML) to make proper statistical inference. An unstructured covariance matrix will be used to model the correlation among repeated measurements and hence avoids the potential bias that could result from the use of specific structured covariance models. If the unstructured covariance model fails to converge with the default Newton-Raphson algorithm, the Fisher scoring algorithm or other appropriate methods can be used to provide initial values of the covariance parameters. In the rare event that none of the above methods yield convergence, a structured covariance such as Toeplitz can be used to model the correlation among repeated measurements. In this case, the empirical option will be used because the sandwich variance estimator is asymptotically unbiased while the model-based variance estimator can substantially overestimate or underestimate the true variance. The cLDA model uses the maximum likelihood principle to estimate the parameters and account for missing data in an implicit fashion.

Although the baseline measurement is included in the response vector, it is independent of treatment, and hence, the baseline means are constrained to be the same for different treatment groups within the same age and insulin use categories. Of note, in the event that there are no missing data, the estimated treatment difference from the above cLDA model will be identical to that from a traditional longitudinal ANCOVA model, which uses the baseline value as a covariate. However, unlike longitudinal ANCOVA, the cLDA model accounts for variability in the baseline values, thus providing more accurate standard errors and CIs for individual treatment effects. Moreover, this model allows the inclusion of participants who are missing either the baseline or post-baseline measurements, thereby increasing efficiency.

The cLDA method assumes that the mechanism for missing data is missing at random (MAR).

Assessment of the Key Secondary Endpoints

The key secondary endpoints will be evaluated under only the TP estimand analysis approach.

PROTOCOL/AMENDMENT NO.: 059-04

All elements of the TP estimands below are the same as the primary TP estimand except for the treatment comparisons:

Treatment comparison of interest:

For H2 - The effect of being randomized to dose-optimized ertugliflozin versus placebo.

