9.10 Subgroup Analyses

To determine whether the treatment effect is consistent across various subgroups, the between-group treatment effect for the primary variable will be summarized and plotted within each category of each subgroup. Treatment groups will be consistent with the primary analysis: ertugliflozin (combined doses) and placebo. Subgroups analyses will be performed only for the primary analysis and treatment comparison. The following subgroups will be analyzed:

• Baseline A1C by categories: ≥ or <median A1C

PRODUCT: MK-8835

PROTOCOL/AMENDMENT NO.: 059-04

- Sex (Male, Female)
- Race (White, Black, Asian, American Indian or Alaska Native)
 Participants who report belonging to more than one racial group will each be assigned to the racial group that has the highest risk for Type 2 diabetes in the order of American Indian or Alaska Native, Asian, Black, White [Copeland, K. C., et al 2011].
- Ethnicity (Hispanic or Latino, Not Hispanic or Latino)
- Age at Screening (10 to 14 years of age, 15 to 17 years of age)
- Insulin use at Screening (No, Yes)
- Geographic region (EU, North America, Other)

Under the TP estimand, summary statistics will be provided for each subgroup analysis to include sample sizes, means, medians, standard deviations, and 95% confidence intervals on the differences in means based on a normal distribution.

Under the TE estimand, the subgroup analyses will be based on a repeated measures ANCOVA model including terms for treatment, insulin use, the subgroup, time as a categorical factor, baseline A1C, and the treatment-by-subgroup interaction. Treatment effects and nominal 95% CIs by category for the classification variables listed above will be reported. Formal statistical testing of treatment-by-subgroup interactions will not be performed. Forest plots will be produced for each estimand, which provide the point estimates and 95% CIs for the estimated treatment effect across the categories of subgroups listed above.

Results from the subgroup analyses should be reviewed cautiously. Because sample sizes within subgroups will be smaller than the overall study sample size, estimation may not be precise, and 95% CIs will usually be wide in the subgroup analyses.

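### The TE-estimand subgroup model in Section 9.10 has no treatment-by-time term, so it estimates an average over visits and not the Week 24 effect

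*Combined protocol and SAP*

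**What the plan says.** Section 9.10 states that "the between-group treatment effect for the primary variable will be summarized and plotted within each category of each subgroup", and limits these analyses to the primary analysis and comparison. The primary variable is fixed elsewhere: "A1C: Change from baseline at Week 24" in Section 9.1, and "Change from Baseline in A1C at Week 24 (pooled ertugliflozin 5 mg and 15 mg versus placebo") in Table 6 of Section 9.4.1.

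Under the TE estimand, the subgroup model has "terms for treatment, insulin use, the subgroup, time as a categorical factor, baseline A1C, and the treatment-by-subgroup interaction". Treatment-by-subgroup is the only interaction listed. No visit is named for the reported contrast, and no covariance structure is given. Category-specific effects with nominal 95% intervals go into forest plots.

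The main TE model in Section 9.6.1 is different: "The cLDA model will also adjust for treatment, the age stratum, the insulin use stratum, and the interaction of time by treatment". It uses an unstructured covariance; if that cannot be fitted, "a structured covariance such as Toeplitz can be used to model the correlation among repeated measurements".

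The subgroup analyses are descriptive: "Formal statistical testing of treatment-by-subgroup interactions will not be performed".

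**The concern.** In a repeated measures model, a treatment term without a treatment-by-time term forces the treatment difference to be the same at every visit. The fitted difference is then a precision-weighted average of the visit-specific differences. It equals the Week 24 difference only if the effect is constant over visits, or if the earlier deviations happen to cancel.

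Constancy is doubtful here for two reasons taken from the protocol. Section 4.2.1.1 says "Since A1C reflects average glucose concentrations over the past 3-4 months", so Week 6 may not yet show the full effect. The pooled ertugliflozin regimen also changes after Week 12, when some participants are re-randomized to 15 mg.

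The subgroup estimates will be read beside the overall TE estimate, which is a Week 24 effect. The two would target different quantities, and the subgroup intervals would describe the visit average. A subgroup difference that appears only at Week 24 would be mostly averaged away, although the stated purpose of Section 9.10 is to look for inconsistency of effect. Because the covariance structure is not named, the weights of the average are not fixed in advance either.

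A smaller point is that the listed model omits the age stratum in six of the seven subgroup models (all except the age subgroup), whereas the main TE model has both strata. That mainly affects precision.

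**Working it through.** **Inputs (Section 9.9, TE Estimand Power).** Conditional covariance at Weeks 6, 12 and 24: V = [1.11, 0.8, 0.6; 0.8, 1.17, 0.8; 0.6, 0.8, 2.25]. Cumulative attrition 4%, 8%, 14%. Allocation 110 and 55. Week 24 difference -0.75, SD 1.5. Section 9.10 does not list its visits, so Weeks 6, 12 and 24 are taken from Section 9.9.

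**The plan's own figure.** With 95 and 47 participants, SE = 1.5 × √(1/95 + 1/47) = 0.2675. Power = Φ(0.75/0.2675 − 1.96) = Φ(0.844) = 80.1%, assuming two-sided 0.05. Generalised least squares with V, the attrition and a treatment-by-time term gives a Week 24 SE of 0.264 and power of 81.0%. The stated figure of at least 80% reproduces.

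**Weights of the listed model.** With treatment and categorical time as main effects only, the treatment estimate is w′d. Here d is the vector of visit differences and w = I·1/(1′I·1). With monotone attrition, per participant,

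I = 0.86·V⁻¹ + 0.06·V₍₆,₁₂₎⁻¹ + 0.04·V₍₆₎⁻¹ (padded with zeros).

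The row sums of I are 0.539, 0.343 and 0.145, with total 1.027. Hence w = (0.525, 0.334, 0.141). With complete data (I = V⁻¹), w = (0.505, 0.339, 0.156).

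**Dependence on covariance structure (Week 24 weight).**

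| Structure | Complete data | With attrition |
|---|---|---|
| Unstructured | 0.156 | 0.141 |
| Toeplitz | 0.368 | 0.337 |
| Compound symmetry | 0.333 | 0.305 |
| Heterogeneous compound symmetry | 0.020 | 0.018 |
| AR(1) | 0.416 | 0.382 |
| Heterogeneous AR(1) | 0.106 | 0.096 |
| Independence | 0.333 | 0.314 |
| Heterogeneous independence | 0.202 | 0.188 |
| Equal variances, plan correlations | 0.433 | 0.399 |

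**What the model would report.** The documents give no Week 6 or Week 12 effect, so these time courses are assumptions. All have a Week 24 effect of -0.75.

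| Weeks 6 / 12 / 24 | Unstructured, attrition | Range over the nine structures |
|---|---|---|
| -0.75 / -0.75 / -0.75 | -0.75 | -0.75 |
| -0.70 / -0.75 / -0.75 | -0.72 | -0.72 to -0.73 |
| -0.50 / -0.70 / -0.75 | -0.60 | -0.59 to -0.65 |
| -0.35 / -0.55 / -0.75 | -0.47 | -0.45 to -0.56 |
| -0.80 / -0.85 / -0.75 | -0.81 | -0.79 to -0.82 |

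**Precision (unstructured, attrition).** SE of the average = √[(1/110 + 1/55)/1.027] = 0.163, against 0.264 for Week 24. The ratio is 1.62 (1.56 with complete data), so the intervals are 1 − 0.163/0.264 = 38% narrower. Half-widths are 0.32 against 0.52 in the full sample, and 0.45 against 0.73 in a category holding half of it.

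**Coverage of the true Week 24 effect in a half-sample category.** With s = 0.163 × √2 = 0.230 and bias b, coverage = Φ(1.96 − b/s) − Φ(−1.96 − b/s). For -0.50/-0.70/-0.75, b = 0.148 and coverage is 90%. For -0.35/-0.55/-0.75, b = 0.277 and coverage is 78%.

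**A subgroup difference present only at Week 24.** An assumed gap of 0.40 would appear as 0.40 × 0.141 = 0.06, and at most as 0.40 × 0.433 = 0.17 in any of the nine structures.

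**Simulation.** The set-up was 1,000 trials of 165 participants with complete data and an unstructured covariance. Two subgroups shared effects of -0.30 and -0.60 at Weeks 6 and 12 but had Week 24 effects of 0.00 and -0.75. Mean estimates were:

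- model as listed: -0.36 and -0.47;
- adding treatment-by-time only, read at Week 24: -0.32 and -0.43;
- adding the three-way term with its lower-order terms, read at Week 24: 0.00 and -0.74.

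**The case against.** The strongest reply is that a list introduced as including certain terms need not be complete. Section 9.10 also omits the covariance structure and the visit list, so an analyst might carry the time interactions over from the main model and read the result at Week 24. Section 9 also allows non-confirmatory analyses to be changed in a supplemental SAP before unblinding, and that document may settle the matter. Against this, Section 9.6.1 names time-by-treatment explicitly, while Section 9.10 names a different interaction and not that one. A programmer following the text would fit the wrong model, so the wording needs correction even if the intention was right.

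The size is also open to challenge, and part of that stands. Every time course above is assumed, the sign of the error is not known, and a near-plateau course costs almost nothing (half-sample coverage about 95%). The SE and coverage figures are for the unstructured case. Under Toeplitz the SE ratio is 1.24 to 1.27 and the two coverages are about 93% and 86%; under heterogeneous independence they are 2.2 to 2.3, and about 88% and 67%.

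Finally, if all categories share one time course, the comparison between them is largely preserved and only the level is off. That is true, but a shared time course is something the analysis should be able to examine rather than impose. Section 9.10 does already fit one interaction model per subgroup, so that part of the advice is to keep what is there.

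**Conclusion.** The concern holds. As listed, the TE subgroup model estimates a visit-averaged effect, while Section 9.10 says it reports the effect on a variable defined at Week 24. Week 24 gets about 14% of the weight under the plan's own covariance and attrition with an unstructured fit, and less than half under all nine structures tried. That part does not depend on assumed effects.

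The resulting error does depend on them. It is zero for a constant effect, and it is attenuation of about 0.15 to 0.28 percentage points of A1C (unstructured) under the two slower-onset courses. It reverses direction if the early effect is larger.

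The consequence is confined to descriptive TE subgroup estimates and their forest plot. H1 to H3, the primary TE cLDA and the TP subgroup summaries are untouched. The change should be made, but the main conclusions of the trial do not rest on it.

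**What to change.** In Section 9.10, for the TE estimand:

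- add treatment-by-time, subgroup-by-time and treatment-by-subgroup-by-time terms (treatment-by-time alone is not enough, as the simulation shows);
- state that the Week 24 contrast in each category is what is reported and plotted;
- name the unstructured covariance, with the same convergence fallback as the cLDA;
- include both stratification factors, age and insulin use, as in the main TE model;
- keep one interaction model per subgroup, because sparse categories such as some race groups may not support an unstructured fit of their own.

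The cost is SAP wording and a few model terms on data already collected. In the unstructured case the intervals become about 60% wider (SE ratio 1.62 with the planned attrition, 1.56 with complete data), which is the honest precision for a Week 24 effect. The larger model will be harder to fit where categories are small.

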9.11 Compliance (Medication Adherence)

A day within the Double-blind Treatment Period will be considered a compliant day if the participant takes 1 tablet of ertugliflozin 5 mg/placebo and 1 tablet of ertugliflozin 15 mg/placebo.

If the study treatment eCRF indicates general compliance problems with any double-blinded therapy, the participant will be considered non-compliant for that day regardless of the number of tablets for the assigned treatment(s) and any matching placebo reported.

PROTOCOL/AMENDMENT NO.: 059-04

For each participant, the compliance rate, based on time until study treatment discontinuation, and the adherence rate, based on time until study discontinuation, will be calculated, using the following formulas:

Compliance rate (%) =
$$\frac{\text{Number of Compliant Days}}{\text{Number of Days in the Double-blind Treatment Period}} \times 100\%$$
Adherence rate (%) =
$$\frac{\text{Number of Compliant Days}}{\text{Number of Days in the Study}} \times 100\%.$$

For each participant the "Number of Days in Double-blind Treatment Period" is the total number of days from the first dose of double-blind study treatment to the date of the last dose of study treatment. The "Number of Days in the Study" is the total number of days from Day 1 to the day of study completion or withdrawal from the study.

9.12 Extent of Exposure

The extent of exposure to study treatment will be evaluated by summary statistics and frequencies for the "Number of Days on Therapy" by treatment group (ertugliflozin and placebo).

10 SUPPORTING DOCUMENTATION AND OPERATIONAL CONSIDERATIONS

10.1 Appendix 1: Regulatory, Ethical, and Study Oversight Considerations

10.1.1 Code of Conduct for Interventional Clinical Trials

Merck Sharp & Dohme LLC, Rahway, NJ, USA (MSD)

I. Introduction

A. Purpose

Merck Sharp & Dohme LLC, Rahway, NJ, USA (MSD), through its subsidiaries, conducts clinical trials worldwide to evaluate the safety and effectiveness of our products. As such, we are committed to designing, planning, conducting, analyzing, and reporting these trials in compliance with the highest ethical and scientific standards. Protection of participants in clinical trials is the overriding concern in the design and conduct of clinical trials. In all cases, MSD clinical trials will be conducted in compliance with MSD's global standards, local and/or national regulations (including all applicable data protection laws and regulations), Regulation (EU) 536/2014, the International Council for Harmonisation Good Clinical Practice (ICH GCP) E6 and ICH General Considerations for Clinical Studies E8, and in accordance with the ethical principles that have their origin in the Declaration of Helsinki.

B. Scope

Highest ethical and scientific standards shall be endorsed for all clinical interventional investigations sponsored by MSD irrespective of the party (parties) employed for their execution (e.g., contract research organizations, collaborative research efforts). This Code is not intended to apply to trials that are observational in nature, or which are retrospective. Further, this Code does not apply to investigator-initiated trials, which are not under the full control of MSD.

II. Scientific Issues

A. Trial Conduct

1. Trial Design

Except for pilot or estimation trials, clinical trial protocols will be hypothesisdriven to assess safety, efficacy, and/or pharmacokinetic or pharmacodynamic indices of MSD or comparator products. Alternatively, MSD may conduct outcomes research trials, trials to assess or validate various endpoint measures, or trials to determine patient preferences, etc.

The design (i.e., participant population, duration, statistical power) must be adequate to address the specific purpose of the trial and shall respect the data protection rights of all participants, trial site staff and, where applicable, third parties. Input may be considered from a broad range of stakeholders, including patient advocacy groups/patients representing the trial population, caregivers, and healthcare providers to ensure operational feasibility. Trial design also includes proactive identification of critical to quality factors utilizing a risk-based approach. Plans are then developed to assess and mitigate risks to those factors as appropriate during the trial. All trial protocols are and will be assessed for the need and capability to enroll underrepresented groups. Participants must meet protocol entry criteria to be enrolled in the trial.

2. Site Selection

MSD's clinical trials are conducted globally in many different countries and in diverse populations, including people of varying age, race, ethnicity, gender, and accounting for other potential disease-related factors. MSD selects investigative sites based on medical expertise, access to appropriate participants, adequacy of facilities and staff, previous performance in clinical trials, as well as budgetary considerations. Prior to trial initiation, sites are evaluated by MSD personnel (or individuals acting on behalf of MSD) to assess the ability to successfully conduct the trial. Individuals involved in trial conduct receive training commensurate with their role prior to their becoming involved in the trial.

Where appropriate, and in accordance with regulatory authority guidance, MSD will make concerted efforts to raise awareness of clinical trial opportunities in various communities. MSD will seek to engage underrepresented groups and those disproportionately impacted by the disease under study. MSD will support clinical trial investigators to enroll underrepresented groups and expand access to those who will ultimately use the products under investigation.

3. Site Monitoring/Scientific Integrity

Investigative trial sites are monitored to assess compliance with the trial protocol and Good Clinical Practice (GCP). MSD reviews clinical data for accuracy, completeness, and consistency. Data are verified versus source documentation according to standard operating procedures. Per MSD policies and procedures, if potential fraud, scientific/research misconduct, privacy incidents/breaches or Clinical Trial-related Significant Quality Issues are reported, such matters are investigated. When necessary, appropriate corrective and/or preventative actions are defined and regulatory authorities and/or ethics review committees are notified.

B. Publication and Authorship

Regardless of trial outcome, MSD commits to publish the primary and secondary results of its registered trials of marketed products in which treatment is assigned,

according to the prespecified plans for data analysis. To the extent scientifically appropriate, MSD seeks to publish the results of other analyses it conducts that are important to patients, physicians, and payers. Some early phase or pilot trials are intended to be hypothesis-generating rather than hypothesis testing; in such cases, publication of results may not be appropriate since the trial may be underpowered and the analyses complicated by statistical issues such as multiplicity.

MSD's policy on authorship is consistent with the recommendations published by the International Committee of Medical Journal Editors (ICMJE). In summary, authorship should reflect significant contribution to the design and conduct of the trial, performance or interpretation of the analysis, and/or writing of the manuscript. All named authors must be able to defend the trial results and conclusions. MSD funding of a trial will be acknowledged in publications.

III. Participant Protection

A. Regulatory Authority and Ethics Committee Review (Institutional Review Board [IRB]/Independent Ethics Committee [IEC])

All protocols and protocol amendments will be submitted by MSD for regulatory authority acceptance/authorization prior to implementation of the trial or amendment, in compliance with local and/or national regulations.

The protocol, protocol amendment(s), informed consent form, investigator's brochure, and other relevant trial documents must be reviewed and approved by an IRB/IEC before being implemented at each site, in compliance with local and/or national regulations and ICH Guidelines. Changes to the protocol that are required urgently to eliminate an immediate hazard and to protect participant safety may be enacted in anticipation of ethics committee approval. MSD will inform regulatory authorities of such new measures to protect participant safety, in compliance with local and/or national regulations.

B. Safety

The guiding principle in decision-making in clinical trials is that participant welfare is of primary importance. Potential participants will be informed of the risks and benefits of, as well as alternatives to, trial participation. At a minimum, trial designs will take into account the local standard of care.

All participation in MSD clinical trials is voluntary. Participants enter the trial only after informed consent is obtained. Trial designs include procedures and systems for the identification, monitoring, and reporting of safety concerns. Participants may withdraw from an MSD trial at any time, without any influence on their access to, or receipt of, medical care that may otherwise be available to them.

PROTOCOL/AMENDMENT NO.: 059-04

During trial planning, the need for an independent Data Monitoring Committee (DMC) is assessed. DMC review of data accumulated during the conduct of the trial is integral to the well-being of trial participants.

C. Confidentiality

MSD is committed to safeguarding participant confidentiality, to the greatest extent possible, as well as all applicable data protection rights. Unless required by law, only the investigator, Sponsor (or individuals acting on behalf of MSD), ethics committee, and/or regulatory authorities will have access to confidential medical records that might identify the participant by name.

D. Genomic Research

Genomic research will only be conducted in accordance with a protocol and informed consent authorized by an ethics committee.

E. Trial Results

At the time of providing informed consent and in accordance with local laws and regulations, participants should be informed about the plans for availability of trial results.

IV. Financial Considerations

A. Payments to Investigators

Clinical trials are time- and labor-intensive. It is MSD's policy to compensate investigators (or the sponsoring institution) in a fair manner for the work performed in support of MSD trials. MSD does not pay incentives to enroll participants in its trials. However, when enrollment is particularly challenging, additional payments may be made to compensate for the time spent in extra recruiting efforts.

MSD does not pay for participant referrals. However, MSD may compensate referring physicians for time spent on medical record review and medical evaluation to identify potentially eligible participants.

B. Clinical Research Funding

Informed consent forms will disclose that the trial is sponsored by MSD, and that the investigator or sponsoring institution is being paid or provided a grant for performing the trial. However, the local ethics committee may wish to alter the wording of the disclosure statement to be consistent with financial practices at that institution. As noted above, all publications resulting from MSD trials will indicate MSD as a source of funding.

C. Funding for Travel and Other Requests

Funding of travel by investigators and support staff (e.g., to scientific meetings, investigator meetings, etc.) will be consistent with local guidelines and practices.

V. Investigator Commitment

Investigators will be expected to review MSD's Code of Conduct as an appendix to the trial protocol, and in signing the protocol, agree to support these ethical and scientific standards.

